6.3.2. Open Label Visits

Study visits Weeks 168 through 384/ED should be completed \pm 28 days of the protocol specified visit date, based on the Baseline Visit.

6.3.2.1. Weeks 168, 216, 264, 312, and 360

- Symptom directed physical exam
- Hepatic ultrasound for surveillance of hepatocellular carcinoma
- Body weight
- Vital signs: blood pressure, pulse, respiration rate, and temperature
- Review concomitant medications
- Review adverse events

- Perform open-label study drug accountability
- Dispense open-label TAF
- Blood sample for serum chemistry and liver function tests, hematology, plasma HBV DNA, serum HBsAg (quantitative), HBV serology (HBsAg and reflex HBsAb), virology (resistance surveillance), and serum and plasma for storage
- Estimated creatinine clearance (using the Cockcroft-Gault method)
- Urine sample for urinalysis, pregnancy test (for females of child-bearing potential; in case of a positive urine test, a serum pregnancy test will be done), and for storage

6.3.2.2. Weeks 192, 240, 288, 336, and 384/ED

The ED Visit should be performed within 72 hours (i.e., visit window is within 3 days) of the last study drug dose.

- Symptom directed physical exam (**At Week 240 and 384/ED**, a complete physical exam should be performed)
- Hepatic ultrasound for surveillance of hepatocellular carcinoma

At ED visit, Hepatic ultrasound should be performed only if not done within the prior 24 weeks

- Body weight
- Vital signs: blood pressure, pulse, respiration rate, and temperature
- ECG (subjects must rest quietly in the supine position for a minimum of 5 minutes prior to the recording)
- DXA scan of spine and hip to be performed (within ± 28 days of the expected visit date; at sites in China with DXA capability only)

At ED visit, DXA scan should be performed only if not done within the prior 24 weeks

- Review concomitant medications
- Review adverse events
- Retrieve study drug and perform study drug accountability
- Dispense Open Label TAF (no study drug will be dispensed at Week 384/ ED visit)

- Fasting blood sample for bone biomarkers and metabolic assessment (glucose and lipid panel [total cholesterol, HDL, direct LDL, and triglycerides]) - no food or drinks, except water, at least 8 hours prior to blood collection
- Fasting urine sample for renal biomarkers
- Blood sample for serum chemistry and liver function tests, hematology, plasma HBV DNA, serum HBsAg (quantitative), HBV serology (HBsAb and reflex HBsAg), virology (resistance surveillance), and serum and plasma for storage
- Estimated creatinine clearance (using the Cockcroft-Gault method)
- Blood sample for Fibrotest[®]
- Urine sample for urinalysis, pregnancy test (for females of child-bearing potential; in case of a positive urine test, a serum pregnancy test will be done), and for storage
- **For ED visit prior to Week 144 only, if not performed within the prior 24 weeks:**
Ophthalmologic assessment, including fundoscopic examination with slit lamp and retinal photographs (both eyes) (**substudy subjects only at select sites** - separate consent required)

6.4. Post-treatment Assessments

6.4.1. HBsAg Loss and Seroconversion Subjects

Subjects who discontinue study drug due to HBsAg loss with confirmed seroconversion to anti-HBs on or after the Week 48 visit, will be followed off treatment every 4 weeks for 12 weeks and then per the study visit schedule through Week 384/ED (excluding drug dispensation and accountability).

6.4.2. All other subjects who discontinue study drug

Subjects who have received at least one dose of study drug and permanently discontinue study drug for reasons other than HBsAg loss with confirmed seroconversion to anti-HBs will be followed every 4 weeks for 24 weeks off treatment or up to initiation of alternative, commercially available HBV therapy, whichever occurs first.

6.4.3. Follow up visit assessments (all subjects)

Treatment-free Follow Up Visits should be completed ± 7 days from the protocol-specified visit date, determined by the date the subject discontinued the study drug.

- Symptom directed physical exam
- Body weight
- Vital signs: blood pressure, pulse, respiration rate, and temperature

- Review concomitant medications
- Review adverse events
- Blood sample for serum chemistry and liver function tests, hematology, plasma HBV DNA, serum for storage, HBV serology (HBsAg and reflex HBsAb at Follow Up visits Weeks 12 and 24), and serum HBsAg (quantitative)
- Estimated creatinine clearance (using the Cockcroft-Gault method)
- Urine sample for urinalysis

6.5. Early Discontinuation (ED) from Study

If a subject discontinues study medication dosing for reasons other than HBsAg loss with confirmed seroconversion to anti-HBs (for example, as a result of an AE), every attempt should be made to keep the subject in the study and continue to perform the required study-related visits and procedures. If this is not possible or acceptable to the subject or investigator, the subject may be withdrawn from the study. Early Discontinuation Assessments are described in Section [6.3.2.2](#).

6.6. Criteria for Discontinuation of Study Treatment

Study medication may be discontinued in the following instances:

- Intercurrent illness that would, in the judgment of the investigator, affect assessments of clinical status to a significant degree
- Unacceptable toxicity, as defined in the toxicity management section of the protocol, or toxicity that, in the judgment of the investigator, compromises the ability to continue study-specific procedures or is considered to not be in the subject's best interest
- Subjects with confirmed creatinine clearance of < 30 mL/min at any time during the study will have their study drug permanently discontinued
- Lack of efficacy (virologic failure)
- HBsAg loss with seroconversion to anti-HBs. These subjects should discontinue study drug within 3-6 months following confirmation of seroconversion to anti-HBs. Subjects with HBsAg loss with confirmed seroconversion before Week 48 are not permitted to discontinue study drug prior to the Week 48 visit
- Discontinuation of study drug for subjects experiencing HBsAg loss with confirmed seroconversion to anti-HBs, who have known bridging fibrosis or cirrhosis, should be considered on a case by case basis

- Subject request to discontinue for any reason
- Subject noncompliance
- Pregnancy during the study; refer to [Appendix 6](#)
- Discontinuation of the study at the request of Gilead Sciences, a regulatory agency or an institutional review board or independent ethics committee (IRB/IEC)

6.7. Intensive Pharmacokinetic Substudy (Optional)

A PK substudy will be performed in a subset of subjects (n=16 and up to n=32) at selected study sites. Separate consent for the PK substudy is required. The substudy will include intensive PK profiling in plasma and will be conducted once at either of the Weeks 4, 8 or 12 visits.

Blood samples will be collected at 0 (\leq 30 minutes pre-dose), 5 minutes, 15 minutes, 30 minutes, 45 minutes, 1 hour, 1.5 hours, 2, 3, 4, 5, 8, 12 and 24 hours post-dose.

Subjects participating in the PK substudy should not take their dose on the morning of the PK visit. Study medication will be administered in clinic on the morning of intensive PK. Subjects who have been routinely dosing in the evening will need to switch to a morning dosing regimen at least 10 days prior to the intensive PK visit. In addition, subjects should fast (no food or drinks for a minimum of 8 hours except water for up to 1 hour) prior to the scheduled intensive PK visit

After collection of the pre-dose sample, subjects will be provided a standardized, moderate fat meal (approximately 600 cal, 27% fat; Details can be found in the PK Manual). **Within 5 minutes after consuming the standardized meal**, subjects will be dosed with TAF. Intensive PK sampling at the following time points will occur: 5, 15, 30, 45 minutes, 1, 1.5, 2, 3, 4, 5, 8, 12 and 24 hours post-dose. Subjects will be restricted from further water intake until 2 hours after and food intake until 4 hours after dosing. The date and time of the subject's previous dose will need to be collected in addition to the data at the PK substudy visit.

Details of pharmacokinetic blood sampling procedures and sample management will be documented in the Pharmacokinetic Sample Collection, Processing, Storage, and Shipment Manual.

Subjects participating in the PK substudy (at sites which can process PBMCs) will also be asked to provide a PBMC (pre-dose) sample at the time of the intensive PK substudy.

6.8. Urine, Serum and Plasma for Storage

A portion of the blood samples collected at each visit starting at Baseline will be frozen and stored. These stored blood samples may be used by the Sponsor or its research partners for HBV genotyping/phenotyping assays or their development, for retesting the amount of HBV in the blood, for measurement of antiviral drug levels in the blood, or for future testing to learn more about how the study drug has worked against HBV or clinical laboratory testing to provide additional safety data. No human genetic testing on this sample will be performed.

A portion of the urine samples collected at each visit starting at Baseline will be frozen and stored. These stored urine samples may be used by Sponsor for future renal and bone biomarker testing (in addition to the tests planned for the study).

At the conclusion of this study, these samples may be retained in storage by Gilead Sciences, Inc. for a period up to 15 years.

6.9. Resistance Surveillance

Genotypic sequence analysis of the HBV polymerase/reverse transcriptase (pol/RT) for resistance mutations will be conducted at Baseline for all subjects, and attempted for all viremic subjects (HBV DNA \geq 69 IU/mL) at Week 48 and every 48 weeks until Week 384/ED visit.

At Baseline, resistance surveillance will be conducted by INNO-LiPA Multi-DR v3 (Innogenetics), which will determine the presence of HBV pol/RT mutations known to confer resistance to lamivudine, adefovir, entecavir, clevudine and/or telbivudine.

Every 48 weeks post Baseline (if viremic), resistance surveillance will be conducted by population sequencing of the HBV pol/RT.

As it may not be known at the time of the visit whether a patient is viremic or if it will be their last study visit, a separate virology sample for potential resistance surveillance will be collected at each study visit.

6.10. Hepatic Ultrasound for Hepatocellular Carcinoma Surveillance

Subjects will undergo hepatic ultrasound assessments for HCC surveillance, beginning at Week 96, at 24 week intervals. Subjects who have completed the Week 96 visit (under Amendment 2.1) should begin ultrasound assessments at the next visit at which an ultrasound assessment is included (see [Appendix 2](#) and [Section 6](#) of the Protocol).

6.11. End of Study

The end of this study will be the last subject's last observation (or visit).

7. ADVERSE EVENTS AND TOXICITY MANAGEMENT

7.1. Definitions of Adverse Events, Adverse Reactions, and Serious Adverse Events

7.1.1. Adverse Events

An adverse event (AE) is any untoward medical occurrence in a clinical study subject administered a medicinal product, which does not necessarily have a causal relationship with the treatment. An AE can therefore be any unfavorable and/or unintended sign, symptom, or disease temporally associated with the use of a medicinal product, whether or not considered related to the medicinal product. AEs may also include pre- or post-treatment complications that occur as a result of protocol specified procedures, lack of efficacy, overdose, drug abuse/misuse reports, or occupational exposure. Preexisting events that increase in severity or change in nature during or as a consequence of participation in the clinical study will also be considered AEs.

An AE does not include the following:

- Medical or surgical procedures such as surgery, endoscopy, tooth extraction, and transfusion. The condition that led to the procedure may be an adverse event and must be reported.
- Pre-existing diseases, conditions, or laboratory abnormalities present or detected before the screening visit that do not worsen
- Situations where an untoward medical occurrence has not occurred (e.g., hospitalization for elective surgery, social and/or convenience admissions)
- Overdose without clinical sequelae (see Section 7.6.1)
- Any medical condition or clinically significant laboratory abnormality with an onset date before the consent form is signed and not related to a protocol-associated procedure is not an AE. It is considered to be pre-existing and should be documented on the medical history CRF.

7.1.2. Serious Adverse Events

A **serious adverse event** (SAE) is defined as an event that, at any dose, results in the following:

- Death
- Life-threatening (Note: The term “life-threatening” in the definition of “serious” refers to an event in which the subject was at risk of death at the time of the event; it does not refer to an event that hypothetically might have caused death if it were more severe.)
- In-patient hospitalization or prolongation of existing hospitalization

- Persistent or significant disability/incapacity
- A congenital anomaly/birth defect
- A medically important event or reaction: such events may not be immediately life-threatening or result in death or hospitalization but may jeopardize the subject or may require intervention to prevent one of the other outcomes constituting SAEs. Medical and scientific judgment must be exercised to determine whether such an event is a reportable under expedited reporting rules. Examples of medically important events include intensive treatment in an emergency room or at home for allergic bronchospasm; blood dyscrasias or convulsions that do not result in hospitalization; and development of drug dependency or drug abuse. For the avoidance of doubt, infections resulting from contaminated medicinal product will be considered a medically important event and subject to expedited reporting requirements.

7.1.3. Clinical Laboratory Abnormalities and Other Abnormal Assessments as Adverse Events or Serious Adverse Events

Laboratory abnormalities are usually not recorded as AEs or SAEs. However, laboratory abnormalities (e.g., clinical chemistry, hematology, and urinalysis) that require medical or surgical intervention or lead to IMP interruption, modification, or discontinuation must be recorded as an AE, as well as an SAE, if applicable. In addition, laboratory or other abnormal assessments (e.g., electrocardiogram, x-rays, vital signs) that are associated with signs and/or symptoms must be recorded as an AE or SAE if they meet the definition of an AE or SAE as described in Sections 7.1.1 and 7.1.2. If the laboratory abnormality is part of a syndrome, record the syndrome or diagnosis (e.g., anemia), not the laboratory result (i.e., decreased hemoglobin).

7.2. Assessment of Adverse Events and Serious Adverse Events

The investigator or qualified sub-investigators is responsible for assessing AEs and SAEs for causality and severity, and for final review and confirmation of accuracy of event information and assessments.

7.2.1. Assessment of Causality for Study Drugs and Procedures

The investigator or qualified sub-investigator is responsible for assessing the relationship to IMP therapy using clinical judgment and the following considerations:

- **No:** Evidence exists that the adverse event has an etiology other than the IMP. For SAEs, an alternative causality must be provided (e.g., pre-existing condition, underlying disease, intercurrent illness, or concomitant medication).
- **Yes:** There is reasonable possibility that the event may have been caused by the investigational medicinal product.

It should be emphasized that ineffective treatment should not be considered as causally related in the context of adverse event reporting.

The relationship to study procedures (e.g., invasive procedures such as venipuncture or biopsy) should be assessed using the following considerations:

- **No:** Evidence exists that the adverse event has an etiology other than the study procedure.
- **Yes:** The adverse event occurred as a result of protocol procedures, (e.g., venipuncture)

7.2.2. Assessment of Severity

Severity of adverse events is to be determined based on GSI Grading Scale for Severity of Adverse Events and Laboratory Abnormalities ([Appendix 5](#)). A distinction should be drawn between seriousness and severity of AEs. An AE that is assessed as Grade 4 (potentially life-threatening) should not be confused with an SAE. Severity is a category utilized for rating the intensity of an event: both AEs and SAEs can be assessed as Grade 4. An event is defined as “serious” when it meets one of the predefined outcomes described above in Section [7.2](#).

7.3. Investigator Requirements and Instructions for Reporting Adverse Events and Serious Adverse Events to Gilead or CRO

Requirements for collection prior to study drug initiation:

After informed consent, but prior to initiation of study medication, the following types of events should be reported on the case report form (CRF/eCRF): all serious adverse events (SAEs) and adverse events related to protocol-mandated procedures.

Adverse Events

Following initiation of study medication, collect all AEs, regardless of cause or relationship, until 4-weeks after last administration of study IMP. AEs must be reported to the CRF/eCRF database as instructed.

All AEs should be followed up until resolution or until the AE is stable, if possible. Gilead Sciences may request that certain AEs be followed beyond the protocol defined follow up period.

Serious Adverse Events

All SAEs, regardless of cause or relationship, that occur after the subject first consents to participate in the study (ie, signing the informed consent) and throughout the duration of the study, including the protocol-required post treatment follow-up period, must be reported to the CRF/eCRF database and Gilead Drug Safety and Public Health (DSPH) as instructed. This also includes any SAEs resulting from protocol-associated procedures performed after informed consent is signed. Any SAEs and deaths, regardless of causality, that occur during the post treatment follow-up period or within 30 days of the last dose of study drug, when subject transitions to alternative, commercially available HBV therapy, should also be reported.

7.4. Gilead Reporting Requirements

Depending on relevant local legislation or regulations, including the applicable US FDA Code of Federal Regulations, the EU Clinical Trials Directive (2001/20/EC) and relevant updates, and other country-specific legislation or regulations, Gilead may be required to expedite to worldwide regulatory agencies reports of SAEs, serious adverse drug reactions (SADRs), or suspected unexpected serious adverse reactions (SUSARs). In accordance with the EU Clinical Trials Directive (2001/20/EC), Gilead or a specified designee will notify worldwide regulatory agencies and the relevant IEC in concerned Member States of applicable SUSARs as outlined in current regulations.

Assessment of expectedness for SAEs will be determined by Gilead using reference safety information specified in the investigator's brochure or relevant local label as applicable.

All investigators will receive a safety letter notifying them of relevant SUSAR reports. The investigator should notify the IRB or IEC of SUSAR reports as soon as is practical, where this is required by local regulatory agencies, and in accordance with the local institutional policy.

7.5. Toxicity Management

- All clinical and clinically significant laboratory toxicities will be managed according to uniform guidelines detailed in [Appendix 4](#).
- Grade 3 and 4 clinically significant laboratory abnormalities should be confirmed by repeat testing within 3 calendar days of receipt of results and before investigational medicinal product discontinuation, unless such a delay is not consistent with good medical practice.
- Clinical events and clinically significant laboratory abnormalities will be graded according to the Table for GSI Grading Scale for Severity of Adverse Events and Laboratory Abnormalities ([Appendix 5](#)).
- When restarting investigational medicinal product following resolution of the adverse event, the investigational medicinal product should be restarted at full dose or modified dose that is dependent upon discussion with the Gilead Sciences Medical Monitor.

- Any recurrence of the investigational medicinal product-related Grade 3 or 4 clinical or clinically significant laboratory adverse event following dose interruption mandates permanent discontinuation of investigational medicinal product.
- Administration of study drug may be discontinued due to a clinical or laboratory event. The Gilead Medical Monitor should be consulted prior to dose discontinuation of study drug unless the investigator believes that immediate action is warranted to ensure the continued safety of subject.
- Any questions regarding toxicity management should be directed to the Gilead Sciences Medical Monitor.

7.5.1. Grades 1 and 2 Laboratory Abnormality or Clinical Event

- Continue investigational medicinal product at the discretion of the investigator.

7.5.2. Grade 3 Laboratory Abnormality or Clinical Event

- For Grade 3 clinically significant laboratory abnormality or clinical event, investigational medicinal product may be continued if the event is considered to be unrelated to investigational medicinal product.
- For a Grade 3 clinical event, or clinically significant laboratory abnormality confirmed by repeat testing, that is considered to be related to investigational medicinal product, investigational medicinal product should be withheld until the toxicity returns to \leq Grade 2.
- If a laboratory abnormality recurs to \geq Grade 3 following rechallenge with investigational medicinal product and is considered related to investigational medicinal product, then investigational medicinal product should be permanently discontinued and the subject managed according to local practice. Recurrence of laboratory abnormalities considered unrelated to investigational medicinal product may not require permanent discontinuation.

7.5.3. Grade 4 Laboratory Abnormality or Clinical Event

- For a Grade 4 clinical event or clinically significant Grade 4 laboratory abnormality confirmed by repeat testing that is considered related to investigational medicinal product, investigational medicinal product should be permanently discontinued and the subject managed according to local practice. The subject should be followed as clinically indicated until the laboratory abnormality returns to baseline or is otherwise explained, whichever occurs first. A clinically significant Grade 4 laboratory abnormality that is not confirmed by repeat testing should be managed according to the algorithm for the new toxicity grade.
- Investigational medicinal product may be continued without dose interruption for a clinically non-significant Grade 4 laboratory abnormality (e.g., Grade 4 CK after strenuous exercise, or triglyceride elevation that is non-fasting or that can be medically managed) or a clinical event considered unrelated to investigational medicinal product.

7.5.4. Management of Bone Evaluation

As there is uncertainty surrounding the clinical significance and management of decreases in bone mineral density for chronic HBV- infected patients, Gilead recommends that any subject who has a DXA scan that demonstrates a decrease from baseline of > 5% in bone mineral density of the spine region or the hip region be followed per local medical practice at the discretion of the investigator.

7.5.5. Management of Potential Nephrotoxicity

Creatinine clearance (CL_{Cr}), estimated according to the Cockcroft-Gault formula, will be followed post-baseline during the study. All subjects with estimated $CL_{Cr} < 50$ mL/min must have serum creatinine measured again within 3 calendar days of receipt of results. At the time of this repeat serum creatinine assessment, Cystatin C will also be measured and the estimated glomerular filtration rate (eGFR) by CKD-EPI (cystatin C) will be calculated and compared with the baseline measurement of this parameter. During the double-blind period, any subject, who has a confirmed CL_{Cr} estimated by the Cockcroft-Gault formula < 50 mL/min and also experiences a $> 20\%$ reduction in eGFR by CKD-EPI (cystatin C) from baseline, will be managed as described below:

CKD-EPI (cystatin C) formula adjusted for age and sex:

$$eGFR \text{ (mL/min/1.73m}^2\text{)} = 133 \times \min(\text{Scys}/0.8, 1)^{-0.499} \times \max(\text{Scys}/0.8, 1)^{-1.328} \times 0.996^{\text{Age}} [\times 0.932 \text{ if female}],$$

where Scys is serum cystatin C (mg/L), $\min(\text{Scys}/0.8, 1)$ indicates the minimum of $\text{Scys}/0.8$ or 1, and $\max(\text{Scys}/0.8, 1)$ indicates the maximum of $\text{Scys}/0.8$ or 1.

Subjects meeting the above eGFR criteria (i.e. confirmed $CL_{Cr} < 50$ mL/min by Cockcroft-Gault equation and $> 20\%$ reduction from baseline in eGFR by CKD-EPI equation) will be managed as follows:

- If the CL_{Cr} is confirmed to be ≥ 30 mL/min and < 50 mL/min, the subject will be required to undergo dose modification to every other day dosing of study drug during the double blind period only.
- If the CL_{Cr} is confirmed ≥ 30 mL/min to < 50 mL/min and the subject has undergone dose modification to every other day dosing of study drug and subsequently develops a confirmed $CL_{Cr} \geq 50$ mL/min, the subject may revert to once daily dosing of study drug after discussion with the Gilead Medical Monitor.
- If the CL_{Cr} is confirmed to be < 30 mL/min at any time during the study, the subject will be required to permanently discontinue study drug.

- All subjects with a change from baseline serum creatinine of ≥ 0.4 mg/dL must have serum creatinine repeated, with a concurrent urinalysis and urine chemistry, within two weeks of receipt of results. The following management will be required dependent upon the corresponding creatinine clearance value:
 - If creatinine clearance is < 50 ml/min, or the subject has other clinical and/or laboratory evidence of acute renal failure, the subject will be managed according to the guidance described above.
 - If creatinine clearance is ≥ 50 ml/min and the repeat testing of serum creatinine confirms a Grade 1 or Grade 2 serum creatinine elevation, it is recommended that subject be monitored weekly until the serum creatinine level returns to a value within the normal laboratory range.
- All subjects with negative or trace proteinuria at baseline that develop $\geq 1+$ proteinuria on urinalysis must have a urinalysis repeated, with a concurrent urinalysis and urine chemistry, within two weeks of receipt of results. Upon confirmation of new proteinuria, subjects will be asked to return to the clinic for a scheduled or unscheduled follow up visit for evaluation. It is recommended that the investigator contact the Gilead Medical Monitor to discuss if further consultation with a nephrologist is clinically warranted.

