- To compare the change from baseline in ophthalmologic findings by fundoscopic examination of TAF 25 mg QD versus TDF 300 mg QD at Weeks 24, 48, 72, 96, and 144 in a subset of subjects
- To characterize the pharmacokinetics of TAF and tenofovir (TFV) and determine intracellular concentrations of tenofovir diphosphate (TFV-DP) within peripheral blood mononuclear cells (PBMCs) in subjects receiving TAF or TDF
- To evaluate the comparative open-label efficacy, safety, and incidence of drug resistance mutations of TAF 25 mg QD in subjects initially randomized to TAF 25 mg QD and in subjects sequentially treated with TDF 300 mg QD and then switched to open-label TAF 25 mg QD

Study Design:

This is a randomized, double-blind, non-inferiority study to compare the antiviral activity of TAF 25 mg QD versus TDF 300 mg QD. Approximately 390 subjects will be randomized in a 2:1 ratio (A:B) to the treatment arms and will be stratified by plasma HBV DNA level ($< 7 \log_{10}$ IU/mL, $\geq 7 \log_{10}$ IU/mL – $< 8 \log_{10}$ IU/mL, $\geq 8 \log_{10}$ IU/mL) and oral antiviral treatment status (treatment-naïve vs. treatment-experienced).

Treatment Arm A: 260 subjects TAF 25 mg QD and matched placebo of TDF 300 mg QD

Treatment Arm B: 130 subjects TDF 300 mg QD and matched placebo of TAF 25 mg QD

For China, approximately 150 additional subjects (100 in Treatment Arm A and 50 in Treatment Arm B) will be enrolled for local registration purposes.

The duration of double-blind treatment is 144 weeks (96 weeks under Amendment 2.1). All subjects who complete the double-blind period of treatment are eligible for participation in the open label TAF 25 mg QD extension period for an additional 240 weeks (through Week 384/ED). Subjects already assigned to open-label TAF 25 mg QD at Week 96 per Amendment 2.1 will continue on open-label TAF 25 mg QD through Week 384/ED. For the entire duration of the study, subjects and investigators will remain blinded to the initial treatment regimen to which they were randomized.

Subjects with a confirmed creatinine clearance (CL_{Cr}) < 50 mL/min, and > 20 % decline in eGFR by CKD-EPI (cystatin C), at any time during the double blind period of the study will be required to undergo dose modification to every other day dosing of study drug. Subjects with confirmed creatinine clearance < 30 mL/min at any time during the study will have the study drug permanently discontinued.

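### Protocol 7.5.5 puts the permanent stop at confirmed CLCr below 30 mL/min under a cystatin C condition that the synopsis and 6.6 do not impose

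*Protocol*

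**What the plan says.** Four places in the protocol state the stop.

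- **Synopsis, Study Design:** "Subjects with confirmed creatinine clearance < 30 mL/min at any time during the study will have the study drug permanently discontinued". The Safety part of the synopsis's Criteria for Evaluation repeats it. In both places the more than 20% decline in cystatin C eGFR belongs to a different rule, every-other-day dosing, for subjects who meet the joint criteria "at any time during the double blind period of the study will be required to undergo dose modification".
- **Section 6.6:** "Subjects with confirmed creatinine clearance of < 30 mL/min at any time during the study will have their study drug permanently discontinued". There is no cystatin C condition.
- **Section 7.5.5:** the joint criteria come first, in a sentence that begins "During the double-blind period, any subject, who has a confirmed" and adds the cystatin C requirement. A lead-in then says that subjects with confirmed CLCr below 50 mL/min and a more than 20% "reduction from baseline in eGFR by CKD-EPI equation) will be managed as follows". Three actions follow: every-other-day dosing at 30 to under 50 mL/min, return to daily dosing on recovery to 50 or more, and, below 30 mL/min, "at any time during the study, the subject will be required to permanently discontinue study drug".

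Section 7.5.5 also has a route for any subject whose serum creatinine rises by 0.4 mg/dL or more. It requires repeat tests and then, if CLCr is below 50 mL/min or there is other evidence of acute renal failure, says "the subject will be managed according to the guidance described above".

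**The concern.** Section 7.5.5 is the protocol's section on managing renal toxicity, and it states a compulsory safety stop more narrowly than the other three statements of it. A site that works from 7.5.5 alone could conclude that a subject with confirmed CLCr below 30 mL/min need not stop because cystatin C eGFR has not fallen by more than 20%. The comparator is associated with nephrotoxicity (protocol 1.1), and treatment is blinded for up to 144 weeks, so this stop should read the same wherever it appears. What is at stake is a missed renal discontinuation. Power, type I error and the primary analysis are not affected.

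**Working it through.** The plan gives no figure to reproduce. The check compares the texts and then asks how far apart the two kidney markers must be before the texts give different answers.

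**1. What each text requires for a subject with confirmed CLCr below 30 mL/min**

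| Cystatin C eGFR fall from baseline | Synopsis and 6.6 | 7.5.5 read literally |
|---|---|---|
| More than 20% | Stop | Stop |
| 20% or less | Stop | Lead-in not met; stop not triggered |
| Not calculable | Stop | Lead-in not met; stop not triggered |

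For CLCr of 30 to under 50 mL/min the sections agree.

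**2. Whether another part of 7.5 closes the gap**

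- The 0.4 mg/dL route refers back to the same list and contains no stop of its own.
- The toxicity grades do not force a stop. Appendix 5 makes creatinine above 2.00 and up to 3.00 mg/dL Grade 2, and 7.5.1 leaves continuation at Grades 1 and 2 to the investigator.

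**3. The CLCr fall that is needed** (Cockcroft-Gault, constant age and weight, so CLCr is proportional to 1/creatinine)

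- From the entry floor: (50 − 30)/50 = 40.0%; creatinine ratio 50/30 = 1.67.
- From 80 mL/min: (80 − 30)/80 = 62.5%; creatinine ratio 80/30 = 2.67.

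**4. The cystatin C rise that gives exactly a 20% eGFR fall** (formula in 7.5.5, constant age)

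A 20% fall multiplies eGFR by 0.80 = 1/1.25.

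- Both values at or above 0.8 mg/L (exponent −1.328): 1.25^(1/1.328) = 1.183, a rise of 18.3%.
- Both values at or below 0.8 mg/L (exponent −0.499): 1.25^(1/0.499) = 1.564, a rise of 56.4%.

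**5. An illustrative subject** (assumed values: man, 60 years, 60 kg)

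- Creatinine 1.0 to 2.4 mg/dL. CLCr = (140 − 60) × 60/(72 × 1.0) = 66.7, falling to 66.7/2.4 = 27.8 mL/min.
- Cystatin C 1.00 to 1.13 mg/L. eGFR = 133 × (1.00/0.8)^−1.328 × 0.996^60 = 77.8, falling to 66.1 mL/min/1.73 m², a 15.0% fall.
- Synopsis and 6.6: stop. List in 7.5.5: condition not met. The creatinine rise of 1.4 mg/dL triggers repeat tests and then points back to that list. Creatinine of 2.4 mg/dL is Grade 2.

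**6. Two further ways for 7.5.5 to miss the stop**

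- SAP 7.4.3 says that baseline cystatin C was collected under protocol amendment 2.1 and after, and SAP section 1 also mentions Amendment 1. A subject with no baseline value has no calculable change and cannot meet the lead-in. The number is not given. SAP 1.2 places all China subjects under Amendment 3.1.
- The sentence that sets the joint criteria covers the double-blind period only, while the stop is worded for the whole study. Taken literally, the list does not reach open-label treatment.

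**The case against.** The strongest reply is that the protocol read as a whole does require the stop. Section 6.6 is the section on discontinuation criteria. It gives the CLCr rule as its own item, apart from its item on toxicity as defined in the toxicity section, and the synopsis gives it twice. The 7.5.5 list is also not a strict filter. Its second item covers subjects who have recovered to 50 mL/min or more, the later items open with all subjects who have a given finding, and the stop's own wording spans the whole study. Finally, the 0.4 mg/dL route selects on CLCr alone, and nearly every affected subject would enter it: a 1.67-fold rise is at least 0.4 mg/dL whenever baseline creatinine is 0.6 mg/dL or more (0.6 × 0.67 = 0.4).

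Much of this stands. The intent is clear, no section directs continued dosing, and the back-reference can be read as applying the CLCr tiers without the cystatin C condition. That reading is one of two, however, because the guidance it points to is the conditional list. The opening sentence of 6.6 is permissive, although its CLCr item is mandatory. Clear intent elsewhere is a reason to correct 7.5.5. It does not make the wording there right.

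**Conclusion.** The concern holds. Section 7.5.5 as written makes a mandatory renal stop depend on a cystatin C condition that the synopsis and 6.6 do not contain. It is best described as an internal inconsistency, with the bullet misplaced, since nothing suggests a different intended policy.

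The practical size is small. Where a baseline cystatin C value exists, creatinine must rise well over 1.5-fold while cystatin C rises only modestly, and the documents give no frequency for that. The thresholds assume constant age and weight, and cystatin C values that stay on one side of 0.8 mg/L. The worked subject uses assumed values. A missed stop also requires a site to rely on 7.5.5 without consulting 6.6 or the synopsis. It should be fixed, as a minor safety-text correction.

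**What to change.** Take the below-30 mL/min item out of the list governed by the joint criteria. State it as a separate rule: any subject with confirmed CLCr below 30 mL/min, in the double-blind or the open-label period, permanently discontinues study drug regardless of cystatin C eGFR. Place it above the 0.4 mg/dL item so that the back-reference there picks it up. Leave every-other-day dosing at 30 to under 50 mL/min under the cystatin C condition.

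The cost is one moved and slightly reworded bullet, in the next amendment or a clarification letter to sites. No data, visits or assays are added.
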